5.5 Analysis Visit Windows

Efficacy, safety, and PK assessments will be summarized by analysis visit as presented in Table 2 below.

Table 2 Analysis Visit Windows

| Analysis Visit | Target Study Day | Study Day Interval |
|------------------------|------------------|--------------------|
| Baseline (Day 1) | 1 | ≤ 1 |
| Day 1 Post First Dose* | 1 | 1 |
| Week 2 | 15 | 2 – 49 |
| Week 12 | 85 | 50 – 133 |
| Week 26 | 183 | 134 – 231 |
| Week 40 | 281 | 232 – 310 |

*For ECG and PK assessments only; other assessments post-first dose on Day 1 will go to the Week 2 analysis visit window.

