3.1.1 Open-label Treatment Period (40 Weeks)

The Week 12/EOT visit of the antecedent study (ACP-2566-003) generally serves as the Baseline visit (Visit 1) of the present study.

Those subjects for whom it is not possible to use the Week 12/EOT visit of the antecedent study (ACP-2566-003) as the Baseline visit (Visit 1) may be re-evaluated for study eligibility at the Baseline visit of the present study, with approval by the Sponsor or Medical Monitor. Those subjects will have blood drawn for Baseline values 3 to 14 days before the Baseline visit. These subjects include: 1) those who were discontinued from Study ACP-2566-003 before completion because of the COVID-19 public health emergency; and 2) those who completed Study ACP-2566-003, but were prevented from entering this study because of the COVID-19 public health emergency.

All efficacy assessments (except the CGI-I) will be completed at the Baseline visit prior to administration of the first dose of study drug in the present study ([Table S-2](#)).

The first dose of study drug for the present study is intended to be administered after all Baseline assessments are completed. Since in most cases, the subject will have taken the last dose of study drug from the antecedent study on the morning of the Baseline visit for this study, the first dose of study drug for this study will then be administered either as an evening dose after the Baseline visit has been completed or on the following day. A triplicate electrocardiogram (ECG) must be performed 2-3 hours after the first dose and a PK sample will be taken upon completion of the ECG.

Study drug must be discontinued at any time in the study in the event that a post-enrollment QTcF duration of ≥ 500 ms or an increase of ≥ 60 ms compared to the average QTcF interval at Baseline of the present study (before dosing) is observed. For visits at which more than one ECG is completed, the average QTcF interval of all legible ECGs will be used to determine the QTcF interval for that visit.

The dose will be administered according to [Section 5.1.3](#). Dosing is twice a day, once in the morning and once in the evening.

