5.3 Study Day

If the date of assessment occurs on or after the first dose date, then study day will be calculated as (date of assessment – date of first dose) + 1. If the date of assessment occurs prior to the first dose date, then study day will be calculated as (date of assessment – date of first dose). There is no study day 0.

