5.5.1 Unscheduled Assessments

Both Scheduled and Unscheduled assessments, including the assessments at early termination visits, will be included for planned timepoint analyses based on the above analysis visit windowing rules. All assessments will be presented in data listings.

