5.5.2 Multiple Measurements within Visit Windows

In the event that more than one assessment falls within a given window, the assessment closest to the target study day will be selected for the by-visit analysis. If two assessments are equidistant from the target study day, then the chronologically last assessment will be used. Exceptions may be made for incomplete assessments, in which case, more complete assessments may be given priority. Details are provided in a separate programming specifications document.

For safety analyses where the extreme values should be selected (e.g., overall post-Baseline minimum, overall post-Baseline maximum, and potentially clinically important values), all

non-missing post-Baseline values should be considered, regardless of whether the value is selected for the by-visit summaries. All assessments will be presented in data listings.

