21. APPENDICES

21.1 Schedule of Assessments

| Period | Baseline | Open-label Treatment Period | | | | Safety Follow-up ^k |
|---|--------------------|-----------------------------|----------------|----------------|----------------|-------------------------------|
| | | 2 | 12 | 26 | 40/EOT/ET | |
| Visit Week | 0 | 2 | 12 | 26 | 40/EOT/ET | EOT/ET+ 30 days |
| Visit Number | 1 | 2 | 3 | 4 | 5 | |
| Visit window (days) | N/A | ±3 | ±7 | ±7 | +7 | +4 |
| Type of Visit ^l | Clinic or Off-site | | | | | Telephone or Telemedicine |
| Informed consent | X ^a | | | | X ^a | |
| Inclusion/exclusion criteria | X | | | | | |
| Medical history update | X | | | | | |
| Physical examination ^l | X | X | X | X | X | |
| Vital signs ^b | X | X | X | X | X | |
| Height | X | | | | X | |
| Weight ^l | X ^l | X | X | X | X | |
| 12-lead electrocardiogram (ECG) ^e | X ^c | X | X | X | X ^c | |
| Clinical laboratory tests (hematology, chemistry) ^m | X | X | X | X | X | |
| Urinalysis | X | X | X | X | X | |
| TSH, Free T3, Free T4 | X | | | | X | |
| Serum pregnancy test ^d | X | | X | X | X | |
| Blood samples for pharmacokinetics | X ^e | X ^f | X ^f | X ^f | X ^f | |
| Blood sample for optional analysis for biomarkers ^g | X ^h | | X | X | X | |
| Rett Syndrome Behaviour Questionnaire (RSBQ) | X | X | X | X | X | |
| Clinical Global Impression–Improvement (CGI-I) ⁱ | | X | X | X | X | |
| Clinical Global Impression–Severity (CGI-S) | X | X | X | X | X | |
| Communication and Symbolic Behavior Scales-Developmental Profile™ Infant-Toddler (CSBS-DP-IT) Checklist | X | X | X | X | X | |

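### A measurement taken hours after the first dose on Day 1 can be reported as the Week 2 result and displace one from Days 30–49

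*SAP*

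**What the plan says.** SAP 5.3 makes the date of first dose Day 1: "study day will be calculated as (date of assessment – date of first dose) + 1". SAP 5.5, Table 2 gives Week 2 a target of Day 15 and an interval of Days 2–49. A separate row, Day 1 Post First Dose, is reserved by footnote for ECG and PK. For all remaining measures the same footnote states that "other assessments post-first dose on Day 1 will go to the Week 2 analysis visit window".

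SAP 5.5.1 sends every kind of visit through these windows: "Both Scheduled and Unscheduled assessments, including the assessments at early termination visits, will be included for planned timepoint analyses". Where one window holds several values, SAP 5.5.2 says that "the assessment closest to the target study day will be selected for the by-visit analysis", and for ties: "If two assessments are equidistant from the target study day, then the chronologically last assessment will be used". The one exception offered is discretionary and concerns completeness: "Exceptions may be made for incomplete assessments, in which case, more complete assessments may be given priority". Further detail is left to a programming specification that is not part of the public documents.

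On what should happen around the first dose, Protocol 3.1.1 says: "All efficacy assessments (except the CGI-I) will be completed at the Baseline visit prior to administration of the first dose of study drug". After that dose it plans a triplicate ECG at 2–3 hours and then a PK sample, and nothing else.

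**The concern.** The footnote contradicts the row it modifies: the printed interval begins at Day 2, and the footnote adds part of Day 1. No minimum time on open-label drug is required for a value to count as Week 2. The SAP also treats one moment in two ways. An ECG taken 2–3 hours after the first dose is labelled Day 1 Post First Dose, while vital signs or blood tests taken at that same time would be labelled Week 2.

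Week 2 is the first scheduled visit after the Baseline visit, in a study whose primary objective is safety and tolerability. Two things can go wrong in the by-visit tables. A value from hours after the first open-label dose can stand in for about two weeks of treatment in this study. And a later on-treatment assessment, such as a late Week 2 visit or an early-termination visit, can be dropped from every by-visit row because the Day 1 value is nearer the target. The tables concerned are by-visit observed values and changes from Baseline, by-visit laboratory shifts (SAP 14.2) and by-visit vital-sign PCI counts (SAP 14.3). These are presented by antecedent treatment group as well as overall, so an affected subject weighs more within the smaller group.

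**Working it through.** **Inputs.** Targets and intervals: SAP Table 2. Study day: SAP 5.3. Selection and tie rules: SAP 5.5.2. Scheduled Week 2 visit window of ±3 days: SAP 21.1.

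**Step 1: reproduce Table 2.** Target day = 7 × week + 1:

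- Week 2: 7 × 2 + 1 = 15
- Week 12: 7 × 12 + 1 = 85
- Week 26: 7 × 26 + 1 = 183
- Week 40: 7 × 40 + 1 = 281

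Midpoints between adjacent targets are (15 + 85)/2 = 50, (85 + 183)/2 = 134 and (183 + 281)/2 = 232. With the midpoint day given to the later visit, these return the printed limits 49/50, 133/134 and 231/232. The table is internally regular; only the footnote departs from it.

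**Step 2: apply the selection rule.** Distance = |study day − 15|. For a Day 1 post-dose value it is |1 − 15| = 14. Set against one other assessment of the same measure:

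| Other assessment | Distance from Day 15 | Selected as Week 2 |
|---|---|---|
| None in window | – | Day 1 |
| Day 2 | 13 | Day 2 |
| Days 12–18 (on schedule) | 0 to 3 | The visit |
| Day 29 | 14 (tie) | Day 29, as the later |
| Day 30 | 15 | Day 1 |
| Day 49 | 34 | Day 1 |

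Day 1 therefore loses to any assessment on Days 2–29 and beats any on Days 30–49, which is 49 − 30 + 1 = 20 days. The scheduled window closes on Day 15 + 3 = 18, so a displaced late Week 2 visit would be 30 − 18 = 12 to 49 − 18 = 31 days past its limit.

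**Step 3: one case followed through.** A subject has repeat vital signs after the first dose on Day 1, misses the Week 2 visit and has an early-termination visit on Day 35. The distances are 14 and |35 − 15| = 20, so the Day 1 value is reported as Week 2. Day 35 cannot move to Week 12, which starts on Day 50, so it appears in no by-visit row.

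**Step 4: repeat without Day 1 post-dose values.** A sole assessment on any of Days 30–49 is now selected as Week 2. A subject with only the Day 1 post-dose value has no Week 2 result. Selection is unchanged for every subject with an assessment on Days 2–29, including all on-schedule Week 2 visits.

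**The case against.** The strongest reply is that the design leaves the rule little to act on. ECG and PK are the only procedures planned after the first dose on Day 1, and both have their own row. Baseline efficacy scales come before dosing (Protocol 3.1.1 and 6.1). The first dose is usually an evening dose after the Baseline visit, or is given the next day. Subjects whose Baseline is not the antecedent study's Week 12 visit have Baseline blood drawn 3–14 days beforehand. An affected value must therefore be unscheduled or out of sequence, and displacement further requires nothing for that measure on Days 2–29. All of this stands, and it limits the point to a small one.

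The footnote also keeps post-dose values out of Baseline, whose interval is Day 1 or earlier. That purpose is sound, but it does not require sending the values to Week 2. A value from Days 30–49 is itself a poor Week 2 value, but it does fall within the printed interval and Day 1 does not. The unseen programming specification might handle the case; nothing in the SAP says it overrides the footnote, and the exception for incomplete assessments does not concern time since dosing.

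Two stronger readings are tempting:

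- **Every such value reflects at most one dose.** This is not so for subjects who had trofinetide in ACP-2566-003 and continue it. Direct rollovers have usually taken antecedent study drug that same morning. Nor do the documents show that the error pulls all measures toward no change; for a main-analysis change, a separate pre-dose value must also exist.
- **The COVID-19 provisions make late Week 2 visits likely.** They allow off-site assessments and late entry into the study. They do not widen the Week 2 visit window, and off-site visits should if anything reduce missed ones.

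**Conclusion.** The point holds as a small but definite error in a stated rule. Table 2's footnote contradicts the printed Week 2 interval and, with the closest-to-target rule, lets a value from hours after the first open-label dose be reported as Week 2. For a former-placebo subject that dose is the first trofinetide in either study. For a subject continuing trofinetide the fault is the time label within this study, not a lack of exposure.

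The day ranges are exact and rest only on the rules as printed. The number of subjects affected cannot be derived: the documents give no rate of post-dose Day 1 assessments or of missed or late Week 2 visits, and any count would be a guess.

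A reader might infer that the study's safety conclusions are at risk. The documents do not support that. Under SAP 5.5.2, overall post-Baseline minimum, maximum and PCI summaries use every post-Baseline value whether or not it was selected for a visit, and all assessments are listed. No hypothesis is tested, and the protocol's efficacy endpoints are at Week 40. The damage is confined to by-visit summaries. It is worth correcting because the correction is nearly free.

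**What to change.** Replace the Table 2 footnote with:

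*For ECG and PK assessments only; other assessments made after the first dose on Day 1 are not assigned to Baseline or to any by-visit window, but are included in listings and in overall post-Baseline minimum, maximum and PCI summaries.*

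The printed interval of Days 2–49 is then true as it stands, and post-dose values still stay out of Baseline. Extending the Day 1 Post First Dose row to all measures is less attractive: it would conflict with the ECG-and-PK restriction and add a nearly empty row to the laboratory, vital-sign and efficacy tables.

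The cost is one sentence and one programming condition. The downside is that a subject whose only value in the window is a Day 1 post-dose value will have no Week 2 value. No safety information is lost, because listings and overall summaries keep it. The change does not address the width of the window: a Day 2 value, 13 days from target, remains eligible for Week 2.

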5.5.1 Unscheduled Assessments

Both Scheduled and Unscheduled assessments, including the assessments at early termination visits, will be included for planned timepoint analyses based on the above analysis visit windowing rules. All assessments will be presented in data listings.

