1.3 Previous Clinical Experience

Trofinetide showed linear pharmacokinetics (PK) across the dose range tested in pediatric RTT patients. These PK results are in agreement with the data obtained previously in healthy subjects and in adult RTT patients. From a drug metabolism perspective, there was no accumulation, metabolic inhibition, or induction observed during treatment. For subjects treated with 50 mg/kg twice daily (BID), median maximum (peak) observed drug concentration (C_{\max}) was 17.7 $\mu\text{g/mL}$ and median $\text{AUC}_{0-12\text{ss}}$ was 139.4 $\mu\text{g/mL}\cdot\text{h}$. For subjects treated with 100 mg/kg BID, median C_{\max} was 52.6 $\mu\text{g/mL}$ and median $\text{AUC}_{0-12\text{ss}}$ was 338.6 $\mu\text{g/mL}\cdot\text{h}$. For subjects treated with 200 mg/kg BID, median C_{\max} was 82.2 $\mu\text{g/mL}$ and median $\text{AUC}_{0-12\text{ss}}$ was 505.1 $\mu\text{g/mL}\cdot\text{h}$. The geometric mean of the apparent terminal elimination half-life ($t_{1/2}$) varied from 5.3 h to 6.1 h across the three dosing groups.

Trofinetide has exhibited a favorable safety and tolerability profile in two studies in subjects with Rett syndrome. Study Neu-2566-Rett-001 (NCT01703533) was a Phase 2 study of trofinetide in 56 adolescent and adult females with RTT (Glaze et al. 2017). Subjects were randomized 2:1 to 35 mg/kg trofinetide BID or placebo for 14 or 28 days (Cohorts 0 and 1, respectively) or 70 mg/kg trofinetide BID or placebo for 28 days (Cohort 2). Both dose levels were well-tolerated in this study, and no time- or dose-dependent adverse events (AEs) were apparent. The most common AE across all treatment groups was diarrhea (39% in the combined 35 mg/kg BID group, 11% in the 70 mg/kg BID group and 15% in the placebo group). The most common AE in the 70 mg/kg BID group was somnolence (17%; vs. 5% in the placebo group and 0% in the 35 mg/kg BID group). Four serious adverse events (SAEs) involving three subjects were reported during the study. In each of these instances, the AEs were deemed unrelated to the study medication. One subject withdrew from the study due to these events while the two subjects had already finished the study medication when their SAEs occurred. Each of these SAEs was deemed to be resolved by study conclusion. The results of this study also provided preliminary evidence of a treatment effect in the 70 mg/kg BID treatment group.

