4.4.2 Handling of Subject Discontinuation During the Treatment Period

Unless the subject has withdrawn consent (or the LAR has withdrawn consent on behalf of the subject) to be contacted for this study, every reasonable effort should be made to complete Visit 5 and the safety follow-up (as outlined in [Table S-2](#)) if a subject discontinues prematurely for any reason. All information will be reported on the applicable pages of the electronic case report form (eCRF).

If a subject is discontinued from the study because of an AE, every reasonable attempt should be made to follow the subject until the AE resolves or until the Investigator deems the AE to be chronic or stable. For subjects who continue to be followed for safety, SAEs should continue to be reported as described in [Section 7.3.2](#). All SAEs will continue to be followed until such events have resolved or the Investigator deems them to be chronic or stable.

Pharmacokinetic samples will also be collected, if possible, at any ET visit or the visit immediately following any SAE or following any AE leading to discontinuation, even if it is an unscheduled visit.

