15. CLINICAL PHARMACOKINETIC AND PHARMACODYNAMIC ANALYSES

For trofinetide-treated subjects, whole blood concentration for trofinetide will be listed. Whole blood concentration data for trofinetide will be summarized for the PK Analysis Set at each visit using descriptive statistics. Concentrations that are below the limit of quantification (BLQ) will be displayed as “BLQ” in the data listings and imputed as 0 for computing summary statistics.

If data allow, population PK and PK/PD analyses will be performed to further characterize the PK profile and exposure response relationship of trofinetide using measures of safety and efficacy parameters. The results of population PK and PK/PD modeling will be presented in a separate report. Trofinetide whole blood concentration data will remain blinded until the unblinding of the clinical database at the end of the study.

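### Early-termination and unscheduled PK samples enter the Week 2 to Week 40 concentration summaries with no condition on time since last dose, so visit means are understated by about the off-drug share

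*SAP*

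**What the plan says.** Four SAP rules act together.

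- **SAP 5.5:** "Efficacy, safety, and PK assessments will be summarized by analysis visit as presented in Table 2 below". Table 2 assigns samples by study day only; Week 12, for example, covers Days 50 to 133 with target Day 85.
- **SAP 5.5.1:** "Both Scheduled and Unscheduled assessments, including the assessments at early termination visits, will be included for planned timepoint analyses".
- **SAP 5.5.2:** when a window holds several assessments, "the assessment closest to the target study day will be selected for the by-visit analysis". Time since dose plays no part.
- **SAP 15:** "Whole blood concentration data for trofinetide will be summarized for the PK Analysis Set at each visit using descriptive statistics". Values below the quantification limit (BLQ) are "imputed as 0 for computing summary statistics".

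The PK Analysis Set (SAP 4) needs one measurable concentration per subject. It screens subjects and does not screen samples.

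The protocol supplies the samples in question. Section 4.4.2 asks for PK blood, if possible, "at any ET visit or the visit immediately following any SAE or following any AE leading to discontinuation", including at unscheduled visits, and Section 6.4 repeats this. Neither sets a maximum time since the last dose. Protocol Table 6-1, in contrast, times the Visit 2 to 5 samples relative to dosing on the visit day, at 2–3, 4–6 or 7–11 h.

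**The concern.** A visit row that is meant to hold samples 2 to 11 h after a dose can also hold samples from subjects who stopped drug days before. Those values carry almost no information on exposure under treatment, yet they count fully in the mean and SD and can set the minimum.

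Whole-blood concentration is the first PK endpoint in Protocol 2.3.1, and the by-visit table is the only PK summary that the SAP itself specifies. Weeks 26 and 40 have wider catchments before their target days than Week 2, so the off-drug share tends to grow with time. In a 40-week study, a lower late mean could be taken for falling exposure or poor compliance when it only reflects who had stopped.

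**Working it through.** The plan states no figure on this point, so there is none to reproduce.

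**Inputs from the documents**
- Terminal half-life (Protocol 1.3): the geometric mean "varied from 5.3 h to 6.1 h across the three dosing groups".
- Windows and targets (SAP Table 2): Week 2, Days 2–49, target 15; Week 12, Days 50–133, target 85; Week 26, Days 134–231, target 183; Week 40, Days 232–310, target 281.

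**Step 1: how much drug is left.** Assume simple terminal decline. Relative to the level 2.5 h after a dose, the level at t hours is 2^(−(t − 2.5)/half-life).

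| Time since last dose | Half-life 5.3 h | Half-life 6.1 h |
|---|---|---|
| 24 h | 6.0% | 8.7% |
| 48 h | 0.26% | 0.57% |
| 72 h | 0.01% | 0.04% |

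Against a 9 h sample the figures are higher: 14–18% at 24 h and 0.6–1.2% at 48 h. The value is low after one day and negligible after two, whether or not BLQ is set to 0.

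**Step 2: does the sample get selected?** Take a last dose on Day 60 and an ET sample on Day 65. Day 65 lies in the Week 12 window. The subject has no scheduled Week 12 sample, so the ET sample is her Week 12 value.

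More generally, put scheduled samples on their target days. An ET sample is then selected if it falls in its window before the target. Over Days 2 to 280 that is 13 + 35 + 49 + 49 = 146 of 279 days (52%). On the other days the scheduled sample is nearer the target and is used.

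**Step 3: effect on the mean.** If a share f of a row's samples is off drug, with residual r, the mean is understated by f × (1 − r).

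**Step 4: an illustration of f.** The documents give neither a discontinuation rate nor a lag from last dose to ET. The assumptions are:
- a constant discontinuation rate with total D by Day 281;
- every discontinuing subject gives an ET sample L days after the last dose;
- half-life 5.7 h, with r = 2^(−24L/5.7).

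With S(d) = exp(−λ(d − 1)) and λ = −ln(1 − D)/280, f is the number who stop in time to give an ET sample in the window without a scheduled one, divided by that number plus those still on drug at the target day.

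Worked case: D = 30%, L = 1 day, Week 12.
- λ = 0.3567/280 = 0.001274.
- S(49) = 0.9407 and S(85) = 0.8985.
- f = (0.9407 − 0.8985)/0.9407 = 4.5%.
- r = 5.4%, so the understatement is 4.5% × 0.946 = 4.2%.

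Understatement of the mean for L from 1 to 7 days:

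| Visit | D = 10% | D = 30% | D = 50% |
|---|---|---|---|
| Week 2 | 0.5% | 1.7–1.8% | 3.2–3.4% |
| Week 12 | 1.3–1.6% | 4.2–5.2% | 8.1–9.9% |
| Weeks 26 and 40 | 1.8–2.1% | 5.8–6.9% | 11.0–12.9% |

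**The case against.** **These rows are weak exposure measures anyway.** They are descriptive, untested and not primary. They already pool samples from 2 to 11 h after dosing, and 6.5 h of decline (2.5 h to 9 h) alone takes a concentration to 43–48%. Characterisation of the PK is left to population PK and PK/PD modelling under a separate data analysis plan, and all assessments are listed. This stands and limits the consequence. It does not remove the error: the spread of sampling times is planned, while an off-drug sample lies outside the planned times altogether.

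**The selection rule helps.** SAP 5.5.2 keeps out the ET sample on about half of possible ET days. This stands, and the figures above allow for it.

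**Not every such sample is off drug.** A reader might infer that all ET and post-event samples follow no current dose, or that a post-event sample chosen over a scheduled one must bias the row. The documents do not support either. The protocol samples after any SAE, including in subjects who continue treatment; an ET visit may follow a dose that day; and Protocol 6.4.1 asks for the event sample as soon as possible. Only time since dose separates the cases.

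**Unseen specifications might cover it.** SAP 5.5.2 defers details to a programming document, and table specifications are separate. That reference concerns the choice among several measurements. It does not displace the inclusion rule in SAP 5.5.1, and it would not help where the ET sample is the only one in the window.

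**Conclusion.** The point holds as a gap in the summary rules. By their own terms, SAP 5.5, 5.5.1 and 15 place samples drawn after treatment has stopped in visit rows whose scheduled samples are defined by time after dosing. The mean falls by about the off-drug share of the row.

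The size is small at Week 2 and small to moderate later: about 2% at Weeks 26 and 40 with 10% total discontinuation, 6–7% with 30% and 11–13% with 50%. These figures rest on an assumed constant rate, an assumed lag of 1 to 7 days, ET samples from all who stop, and simple terminal decay. They are illustrations and do not predict this trial's result. No hypothesis test, primary endpoint or population PK analysis is shown to be affected.

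Two stronger readings go beyond the text. A reader might blame the rule that sets BLQ to 0, but the values are close to zero after one to two days under any BLQ rule; including the samples is the cause. A reader might also say that the SAP presents the rows as on-treatment means. It does not; it calls them summaries at each visit.

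**What to change.** In SAP 15, with a cross-reference in 5.5.1, limit the post-Baseline by-visit concentration summaries, and eligibility for selection under 5.5.2, to samples drawn within 12 h after a recorded dose. Apply this alike to scheduled, ET and post-event samples, so that valid on-drug samples of any kind are kept. The limit covers the longest scheduled interval, 11 h. List all other samples with time since last dose.

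Leave the Baseline predose row unchanged. Subjects who re-enter after a COVID-19 interruption, up to 12 months later, have no recent dose, and a 12 h condition would remove them from that row.

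The cost is SAP wording, one derived variable and a slightly smaller n per row. Protocol 6.4 already requires dose and sample times for scheduled samples, and the last-dose time before an SAE or an AE leading to discontinuation. For unscheduled samples, dose times are recorded only if possible, so a few on-drug samples may be listed without being summarised; a count of excluded samples per visit would show this.
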